DATA ANALYSIS	33
SAMPLE SIZE CALCULATION	34
FUTURE PERSPECTIVE	35
PUBLICATION PLAN	35
TABLE STUDY VISITS AND ASSESSMENTS	36
REFERENCES	38
APPENDICES	42
APPENDIX A: MODIFIED POUCHITIS DISEASE ACTIVITY INDEX (MPDAI)	42
Appendix B: SF-36	43
APPENDIX C: PROMIS MEASURE INCONTINENCE	49
Appendix D: PROBE score	50
Appendix E: Subject Diary for Pouchitis	51
APPENDIX F: ADVERSE EVENT DIARY	52
APPENDIX G: DAILY GLUCOSE DIARY	54
APPENDIX H: HYPOGLYCEMIC PROTOCOL AND REPORTING FORM	55

BACKGROUND

Ulcerative colitis (UC) is a chronic inflammatory gastrointestinal disorder, which is limited to the colon and characterized by the involvement of the mucosa only (in contrast to the transmural inflammation seen in CD). UC affects approximately 500.000 Americans, most of them being

primarily young adults (20 - 40 years) but the disease may present at a very early age (5-10 years) or later in life (>60 years). The inflammatory process in UC is primarily localized to the rectum (proctitis) or can extend proximally in a contiguous manner involving the mucosa up to the splenic flexure (left sided colitis) or involving the entire colon (extensive colitis). The key clinical feature is bloody diarrhea. Approximately 20-35% of patients with UC eventually undergo colectomy, which is most frequently performed in conjunction with ileal pouch-anal anastomosis (IPAA, Figure 1) due to a refractory course of UC or histological proven dysplasia. The ileal pouch serves as a reservoir for the stool and improves functional outcomes following IPAA. While colectomy is often

Ileal pouch-anal anastomosis

depicted as a curative surgery for UC,⁷ multiple short- and long-term complications can occur, including pouchitis, which occurs in 40% of patients within the first year after IPAA creation.⁸ Up to 80% of patients will report pouchitis symptoms at some point after IPAA,⁹ with 19% of patients developing a recurrent form of pouchitis.¹⁰ Despite a preoperative diagnosis of UC or indeterminate colitis (IC), an estimated 10% of patients will be diagnosed with a Crohn's-like disease (CLD) of the pouch after IPAA.¹¹ Epidemiologic studies to better define the pouch population are currently underway (headed by [name] at the University of North Carolina). It is estimated that approximately 50.000 – 100.000 patients live with a pouch in the US and 100.000-150.000 in Europe. Thus, the pouch and its associated medical problems, according to the FDA, can be defined as an orphan disease.

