UNMET NEEDS IN POUCH PATIENTS AND RATIONALE FOR A GLP-1 RECEPTOR AGONIST STUDY Treatment of diarrhea in patients with inflammatory bowel diseases including pouch patients is one of the top 10 research questions for patients and clinicians.²⁸ The average daily bowel frequency for a pouch patient is around 6 and 1-2 bowel movements during the night. 13 However, frequently patients have > 8 bowel movements in 24 hours in the absence of significant pouch inflammation. This high bowel frequency in many pouch patients may be due to low GLP-1 and GLP-2 levels leading to postprandial accelerated gastric emptying and increased small bowel motility as shown in ileostomy patients.^{22-24, 29} The fact that most patients report that they experience urgency and need for immediate evacuation of the pouch 10-20 min after meals point towards the absence of the in the literature described neuroendocrine ileocolonic brake mediated by GLP-1. As outlined above, patients with ileostomies or a pouch have low GLP-1 and GLP-2 levels and GLP-1 as well as GLP-2 receptor agonist therapy can decrease gastric and small intestinal motility as well as stool wet weight output by increasing intestinal absorption. 21, 25-27 The only available GLP-2 receptor agonist teduglutide is exclusively approved for patients with short gut syndrome depending on parenteral support.³⁰ Currently a therapy with teduglutide outside of this indication would be cost prohibitive due to a price tag > \$300.000/year. Given the

overall accepted safety profile and affordability of a GLP-1 receptor agonist, this therapy has the potential to re-establish the neuro-endocrine "brake mechanism", which was abolished due to colectomy. By slowing down the stomach-pouch transit time, increasing wet weight absorption of intestinal contents and decreasing irritant effects of bile acids in the pouch GLP-1 receptor agonist therapy would lead to a higher quality of life for pouch patients with high bowel frequency.

STUDY HYPOTHESIS

Liraglutide is a safe and effective therapy to decrease the number of daily bowel movements in pouch patient with higher than usual bowel frequency.

STUDY AIMS

- 1. To evaluate the effects of liraglutide on bowel frequency in patients with an ileo-anal pouch anastomosis (IPAA) and abnormal high bowel frequency and no signs of endoscopically moderate-severe inflammation (pouchitis). Increased bowel frequency is defined as an increased average > 8 bowel daily over a 7-day time period.

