- 2. To study safety, tolerability and quality of life in the trial period of liraglutide vs placebo application
- 3. To collect first data about the efficacy of a liraglutide therapy in patients with an ileo-anal pouch anastomosis (IPAA) and abnormal high bowel frequency in the absence of inflammation for planning a larger phase 3 study in this orphan status patient population

STUDY DESIGN

Randomized, double-blind, 2-period, placebo- controlled, crossover proof of concept study. Ten patients with increased bowel frequency is defined as > 8 bowel daily/week without significant pouchitis* will be randomized to either liraglutide or placebo treatment for 6 weeks (Period 1). Subjects will be randomized 1:1 to 1 of 2 treatment sequences, liraglutide-placebo or placebo-liraglutide, and receive either liraglutide or volume-matched placebo. After a washout period of at least 5 days (the half-life of liraglutide is 11-12 hours, thus the minimal washout period of 5 days is equal to 10 half-life's) patients will be crossed over to the other treatment arm (Period 2). Since high bowel frequency can result in significant malaise and dehydration, patients not responding to the respective therapies in period 1 may be crossed over after 4 weeks of therapy or in period 2 can be terminated early at week 4. The rationale behind the early termination is based on 2 open label cohorts reporting the efficacy of liraglutide or exenatide in patients with high output ileostomies (the patient group the most comparable to the pouch patient population). GLP-1 receptor agonist therapy even at the lowest dose showed an almost immediate effect reducing the ostomy output after 1-3 days in most patients.^{26, 27} Thus, patients not responding to a 4-week therapy with a GLP-1receptor agonist are highly unlikely to respond if the therapy would be continued.

[figure not shown]

Figure 3: Study design

Randomization: Subjects will be randomized 1:1 to 1 of 2 treatment sequences, liraglutide—placebo or placebo—liraglutide, and receive either liraglutide or volume-matched placebo.

STUDY DRUG, SUPPLY OF STUDY DRUG AND RECRUITMENT PLAN

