So far extent of tachyphylaxis of the effects of liraglutide on gastric emptying are inconclusive or not well defined. Liraglutide (1·2 mg, 1·8 mg, or 3·0 mg daily) delays 1-h gastric emptying, as measured by the plasma acetaminophen method (which reflects predominantly the gastric emptying of liquids, not solids) compared with placebo.³¹⁻³⁴ However, tachyphylaxis of the delay of gastric emptying seems to occur over time but the extent is not clear. For liraglutide 3.0 mg daily one study reports complete tachyphylaxis for delay in gastric emptying based on the plasma acetaminophen method after 5 weeks whereas another study, using a scintigraphy method for gastric emptying which includes the emptying of solid food describes partial tachyphylaxis but still significant efficacy compared to placebo after 16 weeks of therapy.^{32, 34} All studies so far have been performed in patients with an intact GI-tract. The question remains if tachyphylaxis occur in patients with low GLP-1 levels and potentially upregulated GLP-1 receptors in the absence of

a colon. In the only available 2 studies analyzing the effects of liraglutide or exenatide on jejunostomy output no tachyphylaxis was reported after 8 weeks(liraglutide) or 1 year (exenatide) of therapy.^{26, 27}

RECRUITMENT PLAN

We estimate to screen 20 - 25 pouch patients/month and randomize 1 patient/month. We expect that all patients will complete the study after randomization. Under the direction of [name], the University of North Carolina has a Multidisciplinary Pouch Clinic that involves gastroenterology and surgery care for pouch-related disorders. We follow approximately 450 patients from throughout the southeast region of the United States that are treated regularly in our clinic.

STUDY MILESTONES

Months	1-4	4-16	16-22
Activities	Start-up of	Recruitment	Follow-up last
	trial		patients
	IRB		Analysis of
	IND/FDA		clinical data

INCLUSION AND EXCLUSION CRITERIA

INCLUSION CRITERIA

- Informed consent will be obtained before any trial-related procedures
- Age > 18 years
- Patients with IPAA and bowel frequency > 8 bowel movements in 24 hours on at least 4
 of 7 days/week and presence of high bowel frequency > 4 weeks despite adequate
 therapy for acute pouchitis or Crohn's like disease of the pouch

EXCLUSION CRITERIA

- Significant pouch inflammation defined as an endoscopic pouch disease activity index
 (PDAI) ≥ 4

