IRB approval for the study will be obtained after the study is funded. The study protocol will be submitted the UNC IRB and the office of Human research ethics (https://research.unc.edu/human-research-ethics). The study will be conducted in accordance with the Declaration of Helsinki, the ICH GCP guidelines. This study will comply with all applicable regulatory and legal requirements, ICH GCP guidelines and the Declaration of Helsinki in obtaining and documenting the informed consent.

ADVERSE EVENTS AND SERIOUS ADVERSE EVENTS

DEFINITIONS

ADVERSE EVENT

An adverse reaction is an adverse event for which the causal relationship between the product and the adverse event is suspected i.e. e.g.:

- any new diagnosis
- any symptom that requires medical clarification or leads to in-patient admission (surgery or accident)
- any suspected adverse drug reaction (ADR)
- any symptom that appears on the patient's medical records
- any event related in time with the application of the study medication and affecting the health of the patient (including laboratory value changes)

Adverse events (AEs) will be recorded at each regular scheduled study visit or study phone contact in the patient record (source document) as well as on a specific AE form on the electronic CRF.

SERIOUS ADVERSE EVENT

A serious adverse event (SAE) is any untoward medical occurrence that at any dose:

results in death

- is life-threatening
- requires inpatient hospitalization or prolongation of existing hospitalization
- results in persistent or significant disability/incapacity

Important medical events that may not result in death, be life-threatening, or require hospitalization may be considered an Serious Adverse Event when, based upon appropriate medical judgement, they may jeopardize the patient or subject or require medical or surgical intervention to prevent one of the outcomes listed in this definition. Suspicion of transmission of infectious agents must always be considered an SAE.

Non-serious adverse events are all AEs that do not fall into any of the above categories.

SUSPECTED UNEXPECTED SERIOUS ADVERSE REACTION

A suspected unexpected serious adverse reaction (SUSAR) is an SAE which is unexpected and regarded as possibly or probably related to the trial/study product by the investigator

UNEXPECTED ADVERSE DRUG REACTIONS

An unexpected adverse drug reaction (ADR) is an adverse reaction, the nature or severity of which is not consistent with the applicable product information.

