On enrolment in the study, the patients will be instructed to contact the investigator if a serious or unexpected AE occurs, so that appropriate measures can be taken.

Any SAE (including death, irrespective of the cause) occurring during or for up to 14 days after the end of the study will be reported without delay, i.e. within 24 hours, irrespective of its relationship with the administration of the study medication (minimum information required: investigator's name/study center, patient number, patient initials, date of first dose, date of last dose, date of event, description of event, causality assessment, and countermeasures).

A specific AE documentation form will be available. In case of an SAE, this will be completed by the PI (sponsor-investigator) as an initial report. The report must contain a detailed description of the symptoms observed and the concomitant treatment administered. Furthermore, the investigator must comment on a possible causative relationship between the AE and the trial medication. Each SAE must be followed until it is resolved or can be explained satisfactorily.

The general procedure for the observation, collection and analysis of drug risks (regulatory affairs) in conformity with the appropriate national Drug Law shall apply without qualification. In accordance with drug safety and national requirements, the PI of the study (sponsor investigator) will inform the Data and IRB of the study and will make sure that the involved persons will obtain adequate information.

The PI of the study (sponsor-investigator) will report to Novo Nordisk all SAEs, SUSARs, and SADRs at the same time such events are reported to regulatory authorities or within 15 days from the sponsor-investigator becoming aware of such adverse events, whichever comes first.

The sponsor-investigator will collect the following information at minimum for each of these events:

- 1. Study name
- 2. Patient identification (e.g. initials, sex, age)
- 3. Event (preferably a diagnosis)
- 4. Drug
- 5. Reporter identification (e.g. Name, or initials)
- 6. Causality
- 7. Outcome might be reported, but this is not mandatory.

ABNORMAL LABORATORY RESULTS

All laboratory values outside of the normal range will be repeated if judged appropriate by the investigator to ensure the validity of the abnormal result. The investigator will document all

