laboratory values on the relevant page of the electronic CRF and will assess the etiology of the clinically relevant abnormal laboratory values.

Clinically relevant abnormal laboratory values are only documented on the AE form of the electronic CRF, if the patient is discontinued, hospitalized, or, in the investigator's opinion, it should be considered as an AE.

Abnormal laboratory results caused by ulcerative colitis should not be reported on the AE form.

Pregnancy

Pregnancy tests will be performed at the screening visit, week 0, week 4 (in case of early cross over), week 6, week 10, and week 12 of the study. Women of child bearing potential will be asked about contraception compliance at each study contact. If there is concern for pregnancy during the study, the subject will be asked to immediately come to the site for a pregnancy test. The PI (sponsor-investigator) will report to Novo Nordisk any pregnancy occurring during the trial period. Reporting of pregnancy by sponsor-investigator should occur within the same timelines described above for reporting of serious adverse events.

WITHDRAWAL OR STOP OF STUDY DRUG CRITERIA

CRITERIA IN INDIVIDUAL CASES

Any patient can withdraw from the study at any time without personal disadvantages and without having to give a reason. The time of withdrawal, the results available up to that time, and, if known, the reason for withdrawal must be documented in the CRF. The investigator can also discontinue the study after considering the risk-to-benefit ratio, if he/she no longer considers the further participation of the patient justifiable. The date of and the primary reason for the withdrawal as well as the observations available at the time of withdrawal are to be documented on the electronic CRF.

Reasons leading to the **withdrawal** of a patient can include the following (primary reason must be determined):

- inclusion criterion not fulfilled, or exclusion criterion fulfilled; coming to knowledge after recruitment
- patient's request
- technical/logistical reasons (e.g. a change in place of residence, not referred by family physician, etc.)
- withdrawals due to adverse events (including non-serious adverse events leading to withdrawal)
- withdrawal to known adverse drug reaction (ADR as listed above), which is defined as severe according to the listed severity criteria (event/symptom prevents normal daily activities).
- Acute gallstone disease confirmed by
 - o Signs and symptoms of acute gallstone disease

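### The bar on recording laboratory abnormalities attributed to ulcerative colitis as AEs does not fit a post-colectomy population and conflicts with the protocol's other AE rules (minor)

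*Combined protocol and SAP*

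**What the plan says.** The Abnormal Laboratory Results section does three things.

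- All laboratory values go on the laboratory page of the electronic CRF, and the investigator assesses the etiology of the clinically relevant abnormal ones.
- A clinically relevant abnormal value reaches the AE form only if the patient is discontinued or hospitalized, or if the investigator considers it an AE.
- The section then closes with "Abnormal laboratory results caused by ulcerative colitis should not be reported on the AE form". It does not define that attribution and makes no exception for seriousness, discontinuation or hospitalization.

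Three other parts of the protocol bear on this.

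- Background: "Ulcerative colitis (UC) is a chronic inflammatory gastrointestinal disorder, which is limited to the colon".
- Causality (under Documentation and Reporting of Adverse Events): the *Possible* grade covers a laboratory abnormality that concurrent disease might also explain. The *Unlikely* grade covers one for which underlying disease is a plausible explanation.
- Documentation and Reporting of Serious Adverse Events: any SAE during the study or in the 14 days after it "will be reported without delay, i.e. within 24 hours, irrespective of its relationship with the administration of the study medication". The investigator completes an AE documentation form for it.

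**The concern.** An AE form should record what happened and then record the judgement about its cause. This rule reverses the order: a judgement that the cause is ulcerative colitis decides whether there is an entry at all. The rule also names a disease of the colon in patients who no longer have one, so each investigator has to decide what it covers.

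Safety is part of the study hypothesis and of Aim 2. Adverse events by body system are a secondary outcome and a listed safety analysis. The Future Perspective section makes the next trial conditional on this one raising no safety concerns. In a ten-patient study the AE listing will be read event by event, so the rule for what enters it should be unambiguous.

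**Working it through.** No calculation applies. The rule depends on no sample size, effect or error rate, and the plan gives no figure to reproduce. The check is to set the texts side by side.

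**1. Does the label fit the population?** The Inclusion Criteria require an IPAA. Background says that patients with the disease may "eventually undergo colectomy, which is most frequently performed in conjunction with ileal pouch-anal anastomosis". The rationale for a GLP-1 receptor agonist is to restore a brake mechanism "which was abolished due to colectomy". Taken with the statement that the disease is confined to the colon, the named cause is a poor match. The conditions the protocol itself discusses in these patients (pouchitis, Crohn's-like disease of the pouch, high bowel frequency) are not named in the rule.

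**2. Can the rule still operate?** Yes, in limited ways.

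- The footnote to Study Design admits mild cuffitis. Isolated cuffitis is given as a ground for exclusion in the Overview of Trial Sequence, so this route is small.
- The Exclusion Criteria let in primary sclerosing cholangitis with liver tests below 1.5 times the upper limit of normal.
- The screening case history records extraintestinal symptoms.

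The liver route is the realistic one. AST, ALT, alkaline phosphatase and bilirubin are measured on study. Expected Adverse Drug Reactions lists cholelithiasis for liraglutide, and Criteria in Individual Cases includes gallstone disease and raised ALT or AST among possible withdrawal reasons. A liver test rise in a patient with sclerosing cholangitis therefore has two candidate explanations, which is what the causality scale is for.

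**3. Follow one such rise through the texts**, assuming the investigator counts it as caused by ulcerative colitis.

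| Situation | What the other text calls for | What the closing sentence says |
|---|---|---|
| Patient continues; investigator would consider it an AE | AE form, by the preceding sentence; then *Possible* or *Unlikely* on the causality scale | Not on the AE form |
| Patient is discontinued or hospitalized | AE form, by the preceding sentence; then a causality grade | Not on the AE form |
| The abnormality is, or is the basis of, a serious event | Report within 24 hours whatever the relation to study drug, on an AE documentation form | Not on the AE form |

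In each row the two instructions differ, and nothing in the protocol says which prevails.

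**4. What is lost and what is kept.** Lost: the AE entry with its severity and causality grades, and its contribution to the count by body system. Kept: the value on the eCRF laboratory page, the etiology assessment if clinically relevant, and the laboratory-change analysis, which is both a secondary outcome and a listed safety analysis. If the patient is withdrawn, the primary reason is also documented on the eCRF.

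**The case against.** The strongest defence is that the closing sentence is simply an exception to the one before it: values pass the gateway unless the baseline disease explains them. It would rarely apply after colectomy, and nothing is lost from the database. Clinical symptoms are not laboratory results, so they still reach the record through the visit question and the AE diary. Much of this stands, and it is why the point is minor. It does not remove the conflict. Read as an exception, the sentence would keep even a laboratory abnormality that led to discontinuation or hospitalization off the AE form, and would leave two grades of the causality scale unused for such results.

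A reader might infer more than the documents support.

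- *That the rule hides safety data.* It does not. All values remain on the eCRF and in the laboratory analysis.
- *That the rule is inert because the colon is gone.* This is not established, given the cuffitis, cholangitis and extraintestinal provisions above.
- *That it suppresses creatinine or CRP changes from dehydration or pouch inflammation.* That requires replacing ulcerative colitis with a broader condition. Study Design ties dehydration to stool frequency: "Since high bowel frequency can result in significant malaise and dehydration". Pouchitis is named separately throughout.
- *That it contradicts SAE reporting in general.* The rule concerns laboratory results, so the collision is confined to the third row of the table. The phrase about any cause in the SAE section qualifies death. Other SAEs are reported regardless of relation to study medication.
- *That the Adverse Event definition makes every laboratory change after dosing reportable.* Its list follows a definition based on suspected causality, and the relevant item also requires an effect on the patient's health.
- *That the liraglutide–placebo comparison of AEs is biased in a known direction or by a known amount.* The documents give no basis for either.

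**Conclusion.** The point holds as a minor defect in safety-reporting wording. The rule is undefined, does not match the population, lacks an exception for serious events or for those leading to discontinuation or hospitalization, and lets attribution remove an event before causality is graded. Its effect is limited to the AE entry and the AE count by body system. Sample size, power and the primary analysis are untouched. How many events would be affected cannot be estimated from the documents and may be none.

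The conclusion rests on two assumptions. First, some investigator would treat sclerosing cholangitis or cuffitis as part of ulcerative colitis, which the protocol neither states nor rules out. Second, the AE documentation form in the SAE section is the same record as the AE form in the laboratory section. If the two are separate, the SAE conflict falls away. The conflicts with the preceding sentence and with the causality scale remain.

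**What to change.** Delete the closing sentence of Abnormal Laboratory Results. Keep the existing gateway to the AE form unchanged (discontinuation, hospitalization or the investigator's opinion). Requiring an AE entry for every clinically relevant worsening would go beyond this defect. Add one line saying that attribution to underlying disease is recorded on the Causality scale and is not a reason to omit an entry. Add another to Documentation and Reporting of Serious Adverse Events saying that the reporting duty has no laboratory exception.

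The cost is a wording amendment and a few more AE forms. No visit, test or analysis changes.
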